7.1.2 Dermatology Life Quality Index (DLQI)

The Dermatology Life Quality Index (DLQI) questionnaire is designed for use in adults (i.e., subjects aged 16 years and above). The questions are designed to be completed with a one week recall period. It is self-explanatory and can be simply handed to the subject who is asked to fill it in without the need for detailed explanation. It is usually completed in one to two minutes. The Children’s Dermatology Life Quality Index (CDLQI) questionnaire is the DLQI that is adapted for use in children (i.e., subjects from age 4 up to age 16).

Both the DLQI and the CDLQI are calculated by summing the score of each question resulting in a maximum score of 30 and a minimum score of 0.

7.2 Safety Assessments

7.2.1 *Physical Exam*

A brief physical examination will be performed to evaluate objective anatomic findings. This physical examination will be performed at Baseline and at Week 12/ET1. Any clinically significant changes in the physical exam from baseline will be recorded as AEs.

7.2.2 *Pregnancy Testing*

Urine pregnancy testing for females 9 years of age and older will be collected at Screening, Baseline, Week 4, Week 8 and Week 12/ET1. In addition to having a negative UPT at Baseline, before the first application of study drug, females 9 years of age and older must be willing to use an acceptable form of birth control during the study. The following are considered acceptable methods of birth control for this study: abstinence with a documented acceptable method of birth control if the subject becomes sexually active, oral contraceptives, contraceptive patches, contraceptive implant, vaginal contraceptive, double-barrier methods (e.g., condom and spermicide), contraceptive injection, Intrauterine Device (IUD), hormonal IUD, permanent contraception, same sex partner or partner who has had a vasectomy. Tubal ligation is not considered to be surgical sterilization; women with tubal ligations will be required to complete UPTs at the required timepoints.

7.2.3 *BOTE Inflammation Score*

Inflammatory reactions around the MC has been associated with imminent resolution of MC (sometimes referred to as “beginning-of-the-end” [“BOTE”] signs). In most cases, clinical features can differentiate between BOTE and LSR. BOTE may be associated with itching, but not pain. BOTE is usually asymptomatic, self-limited, localized to individual MC lesions, and does not require discontinuation of study treatment or additional treatment.

Investigators will assess the treatment area at each scheduled visit and use their medical judgement to differentiate between BOTE and LSRs. The BOTE Inflammation Score will be recorded at each visit. BOTE should not be considered an AE since this is part of normal disease progression.

BOTE Inflammation Score

Score	Global Assessment	Description
0	No inflammation	No evidence of local inflammation
1	Mild	Minimal erythema and/or edema
2	Moderate	Definite erythema and/or edema with or without hemorrhagic crusting
3	Severe	Erythema and edema with definite hemorrhagic crusting
4	Very Severe	Strong reaction spreading beyond the treated area, bullous reaction, erosions

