Inflammatory reactions around the MC has been associated with imminent resolution of MC (sometimes referred to as “beginning-of-the-end” [“BOTE”] sign). The investigator (or designated evaluator) will assess the presence and overall degree of inflammatory reactions at MC lesions at Baseline (pre-dose) and Weeks 2-12. In most cases, clinical features can differentiate between BOTE and LSR. BOTE may be associated with itch, but not pain. BOTE is usually asymptomatic, self-limited, localized to individual MC lesions, and does not require discontinuation of study treatment or additional treatment. LSR is generally more diffuse, associated with significant itch or tenderness, may necessitate discontinuation of study treatment and may need treatment for symptomatic relief (e.g. a topical corticosteroid or topical anesthetic). For very severe LSR, systemic corticosteroids may be considered. Investigators will assess the treatment area at each scheduled visit and use their medical judgement to differentiate between BOTE and LSRs. BOTE Inflammation Score and LSR score will be recorded at each visit. BOTE should not be considered an AE. When LSRs are clinically significant at the application site, the Investigator should report the condition as AE(s).

At Baseline (30 min. post-dose) and Weeks 2 through Week 12 the evaluators will rate LSRs on individual features including erythema, flaking/scaling, crusting, swelling, vesiculation/pustulation, and erosion/ulceration using the BOTE Inflammation Score ([Section 7.2.3](#)).

Local Skin Reaction (LSR) Scores

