7.2.4 Local Skin Reaction Score

The investigator (or designated evaluator) will assess localized skin reactions (LSRs) at Baseline (at least 30 minutes post-dose), and at Weeks 2, 4, 8 and 12. The individual components of LSRs are scored separately on a scale of 0-4, with higher numbers indicating more severe reactions. The individual components include erythema, flaking/scaling, crusting, swelling, vesiculation/pustulation, and erosion/ulceration.

Compared to BOTE, LSR is generally more diffuse, associated with significant itch or tenderness, may necessitate discontinuation of study treatment and may need treatment for symptomatic relief (e.g. a topical corticosteroid or topical anesthetic). For very severe LSR, systemic corticosteroids may be considered.

Investigators will assess the treatment area at each scheduled visit and use their medical judgement to differentiate between BOTE and LSRs. When LSRs are clinically significant in the opinion of the investigator, s/he should report the condition as an AE(s) (e.g. application site erythema, application site edema).

In the event of an LSR, the investigator may choose to initiate a drug holiday for the study drug for up to 2 weeks; treatment with corticosteroids may be ordered during the drug holiday at the investigator's discretion. For very severe LSR, systemic corticosteroids may be considered. The subject should be instructed how many days to hold study drug and site staff should phone the

subject on the planned day of resuming study drug to ensure that the LSR has resolved. If the LSR has not resolved, the drug holiday may be extended as long as the total period of withholding study drug does not exceed 2 weeks. If the LSR has resolved, the subject may resume treatment. If the LSR flares again after re-introduction of study drug, allergic contact dermatitis may be suspected. The subject may again be treated with up to 2 weeks of corticosteroids.

If allergic contact dermatitis is suspected, study drug should be discontinued permanently and an AE of allergic contact dermatitis should be recorded as the reason for discontinuation. Week 12/ET1 assessments should be completed at the time of discontinuation, but the subject should continue in the study and complete study-related visits through Week 24.

Patch testing (see [Section 7.2.5](#) and [Section 20.2](#)) should be offered to the subject.

LSR Score

	Erythema	Flaking/ Scaling	Crusting	Swelling	Vesiculation/ Pustulation	Erosion/ Ulceration

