20.2 APPENDIX II Procedure for Suspected Sensitization

In the event that a subject has a local skin reaction (LSR) severe enough that is felt to be suggestive of allergic contact dermatitis, patch testing may be initiated for confirmation after consultation with the CRO Medical Monitor and with the consent of the subject/caregiver. Once the LSR has been completely resolved for a period of 2 weeks and up to 2 months, patch testing may commence. Novan will provide more detailed patch testing instructions once requested from the CRO Medical Monitor. The site will use a study drug kit already assigned to the subject in order to complete the testing.

For patch testing:

- Discontinue study treatment (see [Section 7.2.4](#) regarding LSRs)
- Document the event as an AE and consult with the CRO Medical Monitor. Detailed instructions for the patch testing will be provided after discussion with the Medical Monitor.
- When applicable, challenge patch testing should be performed after all signs and symptoms of the LSR have been resolved for approximately 2 weeks to 2 months.
- The randomized study treatment will be applied to a naïve area on the participant's back or arm. Use the subject's most recently assigned study drug kit to obtain material for testing.
- The participant will return to the site approximately 48 hours after the application of the patches. Approximately 30 minutes, 24 hours and 48 hours after patch removal, the patch site(s) will be evaluated using the scale below ([Table 2](#)). If the 48-hour reading is equivocal, it is recommended to evaluate the site at 72 to 96 hours after removal. Take photographs if the reaction interpretation is positive or equivocal and transmit them to the Medical Monitor. Further instructions will be given after review of the photos.
- At the last reading, the investigator will make the final interpretation of any challenge reactions. See [Table 3](#) below.

Table 2: Grading System for Patch Test Reactions

Score	Description
+-	Doubtful reaction, faint macular erythema
+	Weak, non-vesicular reaction with erythema, infiltration and papules
++	Strong vesicular reaction with erythema, infiltration and papules
+++	Spreading bullous reaction
-	Negative reaction
IR	Irritant reaction

Table 3: Challenge Reaction Interpretation

Score	Description
Negative	Might include an irritative reaction
Equivocal	Unable to determine
Positive	Reaction definitely due to sensitization

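### BOTE is exempt from AE reporting at every grade, yet its score 4 describes a spreading, bullous, eroding reaction that overlaps LSR grade 4, so such a reaction can be left out of the AE tables

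*Combined protocol and SAP*

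**What the plan says.** **BOTE.** The protocol (synopsis, 4.1 and 7.2.3) describes it in these words: "BOTE is usually asymptomatic, self-limited, localized to individual MC lesions, and does not require discontinuation of study treatment or additional treatment". Section 7.2.3 adds: "BOTE should not be considered an AE since this is part of normal disease progression". The synopsis, 4.1 and SAP section 4 repeat the exemption, and none of them limits it by grade. The scale runs from 0 to 4, and score 4 (Very Severe) reads "Strong reaction spreading beyond the treated area, bullous reaction, erosions".

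**LSR.** Section 7.2.4 sets the contrast: "Compared to BOTE, LSR is generally more diffuse, associated with significant itch or tenderness". Six components are each scored 0 to 4. An LSR becomes an AE when the investigator judges it clinically significant (7.2.4, 9.1).

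**Telling them apart.** At each visit investigators are to "use their medical judgement to differentiate between BOTE and LSRs".

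**Cross-reference.** Section 4.1 says that "the evaluators will rate LSRs on individual features including erythema, flaking/scaling, crusting, swelling, vesiculation/pustulation, and erosion/ulceration using the BOTE Inflammation Score", and points to 7.2.3.

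**SAP.** Section 13.1 restricts the AE summaries to TEAEs. Section 13.3 defines events of special interest by application-site TEAEs, a moderate BOTE score, or any LSR component of at least 1.

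**The concern.** The top grade of the BOTE scale does not fit the text that defines BOTE. That text says usually localized and in no need of extra treatment; score 4 says spreading, bullous and eroded. An evaluator who sees such a reaction finds it listed on the BOTE scale and finds a rule beside the scale that BOTE is not an AE. Administration-site reactions are the only AEs that protocol 1.1.4 regards as clearly associated with SB206. A rule that lets a severe one go unreported as an AE therefore touches the part of the safety record that matters most for this product. At stake is the completeness of the AE listing and the TEAE tables for severe local reactions.

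**Working it through.** The documents give no figure to reproduce. The check is a comparison of wording, followed by what arithmetic can say about size.

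1. **Definition against scale.** The BOTE description in 7.2.3 says usually localized to lesions. Score 4 in the table below it requires spread beyond the treated area. The word *usually* leaves room for exceptions, but nothing says how an exception is to be handled.

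2. **Overlap with LSR.** In 7.2.4 diffuseness is the sign that points to LSR. Grade 4 for erythema, scaling, crusting and swelling is extension outside the treatment area, and separate components cover vesiculation and erosion. One reaction can therefore meet BOTE score 4 and several high LSR grades.

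3. **Timing.** Table 1, footnote 4, has both scores taken post-dose from Visit 3 through Visit 6 (Weeks 2 to 12). A BOTE score does not replace the LSR score, so the signs should appear in the LSR data in any case.

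4. **The AE decision.** What the label governs is the AE call. Called a clinically significant LSR, the reaction is an AE (7.2.4, 9.1). Called BOTE, it is not (7.2.3). Section 9.1 lists significant LSRs and scarring among the events to capture and does not mention BOTE. No section links a BOTE score of 3 or 4 to AE assessment.

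5. **The 4.1 cross-reference.** BOTE is one global score and cannot rate six features separately. Sections 7.2.4 and SAP 4 keep the scales apart, so 4.1 is an error of reference.

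6. **The SAP special-interest row.** On the scale, moderate is the label of score 2. Read literally, section 13.3 omits scores 3 and 4. SAP section 12 groups 2, 3 and 4 as moderate to very severe, so the intent may have been moderate or worse, but 13.3 does not say so.

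7. **Size.** With the planned groups of 227 and 113, one subject is 1/227 = 0.44 percentage points on SB206 and 1/113 = 0.88 on vehicle. Overall TEAE incidence moves by that amount only if the subject has no other TEAE. The number of score-4 reactions, and their split by arm, is not given, so no total follows.

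**The case against.** The strongest reply is that the plan has several other ways to catch such a reaction.

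- LSR components are scored in parallel, and any component of at least 1 already makes the subject an event of special interest.
- The text offers clinical discriminators: BOTE may itch but is not painful, and LSR is more diffuse. By these, a spreading bullous reaction points to LSR.
- AEs reported by the subject must be recorded (9.1), an AE form is expected where applicable when a new therapy starts (8.7), and significant physical-examination changes at Week 12/ET1 are AEs (7.2.1). A treatment hold can also follow from subject-reported intolerance (4.1).
- BOTE is a safety endpoint (3.4), with a Safety Population shift table, a summary table and a listing in the SAP. The DSMB is to review all available unblinded safety data (13.2), not AEs alone.

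All of this stands. It makes the omission possible rather than likely, and it means the signs remain visible to safety review. It does not remove the unqualified exemption in 7.2.3, and BOTE tables are not AE reporting.

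A reader might also infer that the loss must fall on the SB206 arm, because all seven AE-related stops in Phase 2 were on active treatment and six were application-site reactions. The documents do not support that inference. All seven were in twice-daily groups, and 1.2.2 reports none at 12% once daily, the regimen tested here. Active subjects numbered 47 + 48 + 47 + 48 = 190 of 256. By chance alone, all six application-site stops would be on active with probability (190·189·188·187·186·185)/(256·255·254·253·252·251) = about 16%. No BOTE scores by arm are given. Nor do the documents report any case of contact sensitization; the patch-test appendix is a contingency procedure, and its top grade, "Spreading bullous reaction", belongs to a different assessment.

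**Conclusion.** The contradiction holds and should be corrected. As written, a reaction scored 4 on the BOTE scale and labelled BOTE can be left out of AE reporting and the TEAE tables, even though it has the features by which the protocol recognises an LSR. A reader might go further and conclude that the worst local reactions vanish from the safety record, or that the comparison is biased in favour of SB206. Neither follows: the LSR and BOTE outputs retain the signs, and neither the size nor the direction of an under-count can be estimated from the documents. The conclusion assumes only that some investigators will apply the exemption as it is worded.

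**What to change.** 1. Reconcile the synopsis, 4.1, 7.2.3, 7.2.4 and SAP section 4 so that the AE exemption covers only reactions meeting the protocol's own BOTE description. State that a BOTE score of 4 does not by itself exempt a reaction from AE assessment.
2. Correct 4.1 so that LSR features are rated on the LSR score in 7.2.4.
3. Word the BOTE criterion in SAP 13.3 as moderate or worse (scores 2 to 4).
4. Query each BOTE score of 4 without a matching AE record before the Week 12 database freeze (protocol 11.1, SAP section 6).

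How such reactions bear on holding, stopping, treatment and patch testing is for the sponsor to reconcile; nothing is proposed here. The cost is protocol and SAP wording, a note to sites and one data query, with no added visits and no change to the efficacy analysis. The reported AE rate may rise slightly.

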7.2.4 Local Skin Reaction Score

The investigator (or designated evaluator) will assess localized skin reactions (LSRs) at Baseline (at least 30 minutes post-dose), and at Weeks 2, 4, 8 and 12. The individual components of LSRs are scored separately on a scale of 0-4, with higher numbers indicating more severe reactions. The individual components include erythema, flaking/scaling, crusting, swelling, vesiculation/pustulation, and erosion/ulceration.

Compared to BOTE, LSR is generally more diffuse, associated with significant itch or tenderness, may necessitate discontinuation of study treatment and may need treatment for symptomatic relief (e.g. a topical corticosteroid or topical anesthetic). For very severe LSR, systemic corticosteroids may be considered.

Investigators will assess the treatment area at each scheduled visit and use their medical judgement to differentiate between BOTE and LSRs. When LSRs are clinically significant in the opinion of the investigator, s/he should report the condition as an AE(s) (e.g. application site erythema, application site edema).

In the event of an LSR, the investigator may choose to initiate a drug holiday for the study drug for up to 2 weeks; treatment with corticosteroids may be ordered during the drug holiday at the investigator's discretion. For very severe LSR, systemic corticosteroids may be considered. The subject should be instructed how many days to hold study drug and site staff should phone the

subject on the planned day of resuming study drug to ensure that the LSR has resolved. If the LSR has not resolved, the drug holiday may be extended as long as the total period of withholding study drug does not exceed 2 weeks. If the LSR has resolved, the subject may resume treatment. If the LSR flares again after re-introduction of study drug, allergic contact dermatitis may be suspected. The subject may again be treated with up to 2 weeks of corticosteroids.

If allergic contact dermatitis is suspected, study drug should be discontinued permanently and an AE of allergic contact dermatitis should be recorded as the reason for discontinuation. Week 12/ET1 assessments should be completed at the time of discontinuation, but the subject should continue in the study and complete study-related visits through Week 24.

Patch testing (see [Section 7.2.5](#) and [Section 20.2](#)) should be offered to the subject.

LSR Score

	Erythema	Flaking/ Scaling	Crusting	Swelling	Vesiculation/ Pustulation	Erosion/ Ulceration
0	Not present	Not present	Not present	Not present	Not present	Not present
1	Slightly pink	Mild, limited	Isolated crusting	Minimal, limited	Fine vesicles	Superficial erosion
2	Pink or light red	Moderate	Crusting < 50%	Mild, palpable	Scant transudate or exudate	Moderate erosion
3	Red, restricted to treatment area	Coarse	Crusting > 50%	Moderate	Moderate transudate or exudate	Marked, extensive
4	Red extending outside treatment area	Scaling extending outside treatment area	Crusting extending outside treatment area	Marked swelling extending outside treatment area	Marked transudate or exudate	Black eschar or ulceration

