Subjects will visit the clinic at Screening/Baseline, Week 2, Week 4, Week 8, Week 12, and Week 24. Subjects will be contacted via phone on Day 2 to collect subject information on early dose reactions. At Weeks 16 and 20, subjects will be contacted via phone to capture information regarding MC recurrence and AEs; at Week 24, the subject will be seen at the site for a final study visit. Subjects who discontinue the study prior to the Week 12 visit due to adverse events or other reasons will be asked to complete the Week 12 visit assessments; this will be recorded as an Early Termination (ET1) visit. No study drug treatment will be provided after the Week 12 visit. Subjects who discontinue from the study after Week 12 but prior to Week 24 will be asked to come to the site to complete Week 24 assessments; this visit will be recorded as an ET2 visit.

Safety assessments include BOTE Inflammation Scores, Local Skin Reaction Scores (LSRs), adverse event collection, including scarring/keloid and urine pregnancy tests (UPTs). Safety assessments will be completed at specified site visits through Week 12. After Week 12, safety information for ongoing AEs and new AEs will be collected, along with information regarding MC recurrence. For the purpose of this study, a recurrence of MC will be documented as an AE.

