7.1 Efficacy Assessments

7.1.1 *Molluscum Contagiosum Lesion Counts*

Molluscum contagiosum is a viral infection characterized by small, discrete, waxy, skin-colored, dome-shaped papules, an average of 3–5 mm in diameter. The papules may be umbilicated and contain a caseous plug. When the lesions are squeezed or traumatized, a creamy, grey-white material can be extruded. If the investigator cannot clearly differentiate the lesions as is the case for agminated (clustered lesions) this should be counted as one lesion. If the investigator can differentiate and count the umbilical tops separately, each lesion should be counted separately. The

investigator should be consistent with the method of recording agminated lesions throughout the study.

For the purpose of this clinical trial, only active MC lesions are counted. Treatable lesions are any active (raised, palpable) MC lesions that are dome-shaped, pearly and shiny white top centered papules that are at least 2 cm away from the ocular region.

All study personnel who will perform lesion counts must pass the study training including lesion count training. Training on how to accurately count the number of MC lesions will be provided.

Mapping of lesions: At every visit from Baseline through Week 12, all lesions should be recorded on the body map and will clearly note the location of each lesion or agminated lesion. The lesion map is intended to assist study personnel in performing lesion counting and scar/keloid assessment.

Definition of Clearance: For the purpose of this study, “clear” means resolution of the active (raised, palpable) treatable molluscum lesion(s). After resolution, the residual surface changes such as pitted scar (indentation) < 1 mm in depth at the molluscum lesion area (<5 mm in diameter), hyper or hypopigmentation may remain. As these are considered part of the normal healing, they will not be captured as adverse events. Refer to the lesion count training for details.

The same evaluator should perform lesion counts at Screening, Baseline, and Weeks 2, 4, 8 and 12/ET1. In the event that this is not possible due to unforeseen circumstances, a different evaluator may evaluate the subject. The evaluator must pass the study training including lesion count training. It is particularly important to ensure the same evaluator performs the Baseline and Week 12/ET1 for lesion count for a subject and also Baseline and Week 24/ET2 assessment for scarring/keloid scarring.

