7.2.5 Patch Testing

In the event that a subject has an LSR that is felt to be suggestive of allergic contact dermatitis, patch testing may be initiated to confirm. This should be offered to the subject/caregiver. If the subject/caregiver consents to patch testing and once the LSR has been completely resolved for a period of 2 weeks and up to 2 months, patch testing will commence. Novan will provide the patch testing instruction once requested from the CRO medical monitor. Additional drug product for

patch testing may be supplied through IWRS if the currently assigned subject's investigational product has been assignment was > than 60 days of the patch testing date(s).

If allergic contact dermatitis is suspected, study drug should be discontinued permanently and an AE of allergic contact dermatitis should be recorded as the reason for discontinuation. Week 12/ET1 assessments should be completed at the time of discontinuation, but the subject should continue to participate in the study and complete study related visits through Week 24.

In the event of suspected allergic contact dermatitis, photographs may be taken of the affected area(s) and transmitted to the CRO medical monitor for review prior to initiating patch testing.

See [Section 20.2](#) for further information.

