7. NOTATION OF TREATMENT GROUPS AND VISITS

Analysis visits

Baseline is defined as the last nonmissing value recorded prior to the first application of study drug. If time is not recorded and the assessment was on the same day as the first application of study drug, then it will be assumed the assessment occurred prior to the application of study drug. The baseline record will have an analysis visit of “Baseline”.

For all evaluations of all parameters, assessments will be analyzed according to the visit at which they occurred (i.e., per the eCRF visit label). In order to account for the fact that the Week 12 and Early Termination visits are collected on the same eCRF in the database, a check against the Study Exit form will be made to determine if the visit is a Week 12 or an Early Termination Visit. If the visit is an Early Termination visit, then the visit will be mapped according to the table below. If there is no corresponding Study Exit form on the same date, then it will be considered a Week 12 visit. If there is no assessment in a given visit, then the following visit windows will be applied to determine if an unscheduled visit may be used:

Visit	Analysis Visit	Target Study Day	Study Day Analysis Window
Week 2 (± 3 days)	Week 2	15	Day 12 to 22
Week 4 (± 5 days)	Week 4	29	Day 23 to 43
Week 8 (± 5 days)	Week 8	57	Day 44 to 71
Week 12 (± 5 days)	Week 12	85	Day 72 to 98

Days are measured from the date of randomization. Study days corresponding to measurements are calculated as:

- Assessment date – date of randomization + 1, if assessment date is on or after the date of randomization.
- Assessment date – date of randomization, if measurement date is before the date of randomization.

In the event of multiple unscheduled records falling in the same analysis window, the assessment which is closest to the target study day will be chosen for analysis.

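### A lesion count taken when drug is stopped for suspected contact dermatitis would, if entered on the shared Week 12/ET form, be analysed as Week 12 at any study day

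*Combined protocol and SAP*

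**What the plan says.** **Protocol.** Section 7.2.4 requires a permanent stop of study drug when allergic contact dermatitis is suspected, and adds: "Week 12/ET1 assessments should be completed at the time of discontinuation, but the subject should continue in the study". Section 7.2.5 repeats the instruction, "but the subject should continue to participate in the study and complete study related visits through Week 24". The Week 12/ET1 assessments include the lesion count (Table 1; Section 7.1.1: "The same evaluator should perform lesion counts at Screening, Baseline, and Weeks 2, 4, 8 and 12/ET1"). Nothing cancels the scheduled Week 12 visit at Day 85 ±5, and Section 6.3.1 encourages subjects who stop drug for an adverse event to keep to the visit schedule. Elsewhere ET1 belongs to people who leave the study: for those who discontinue before Week 12, Section 4.1 says "this will be recorded as an Early Termination (ET1) visit".

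**SAP 7** (the same rule in all three SAP texts supplied). Assessments are analysed by eCRF visit label. The section notes that "the Week 12 and Early Termination visits are collected on the same eCRF in the database" and uses the Study Exit form to tell the two apart:
- With a Study Exit form: "If the visit is an Early Termination visit, then the visit will be mapped according to the table below".
- Without one: "If there is no corresponding Study Exit form on the same date, then it will be considered a Week 12 visit".

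Beyond early terminations, the window table (Week 12: Day 72 to 98, target Day 85) is applied only to unscheduled records, and only when the scheduled visit has no assessment. The closest-to-target rule is likewise confined to unscheduled records: "In the event of multiple unscheduled records falling in the same analysis window".

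**SAP 10.4** scores a missing response as nonresponse.

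**The concern.** The protocol creates a Week 12/ET1 assessment in a subject who has not left the study. SAP 7 separates Week 12 from early termination only by a form that such a subject will not have on that date. If the assessments are entered on the shared form, a count taken weeks early takes the Week 12 label. The same count from a subject who does leave is mapped by study day.

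The Week 12 count decides the primary endpoint. If the scheduled visit is missed, the early count fills a gap that SAP 10.4 would have scored as nonresponse. If the visit is attended, two Week 12 records exist and SAP 7 does not say which is used. A choice made after unblinding would be a post hoc decision on the primary endpoint.

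**Working it through.** **1. The plan's own figure.** Inputs from SAP 5: 227 SB206 and 113 vehicle subjects, 36% vs 18% clearance, two-sided alpha 0.05. Pooled-variance normal approximation:
- Pooled rate = (113 × 0.18 + 227 × 0.36)/340 = 0.3002
- SE under the null = √[0.3002 × 0.6998 × (1/113 + 1/227)] = 0.0528
- SE under the alternative = √[0.18 × 0.82/113 + 0.36 × 0.64/227] = 0.0482
- z = (0.18 − 1.96 × 0.0528)/0.0482 ≈ 1.59, so power is 94.4% against the stated 94%

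The other two scenarios give 93.4% and 82.8% against 93% and 83%. The arm sizes are therefore used below as stated.

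**2. Rule trace, given entry on the shared form.** Drug stopped for suspected contact dermatitis → Week 12/ET1 assessments that day → subject stays in, so no Study Exit form on that date → SAP 7 labels the record Week 12, with no study-day condition. The window table is not reached, because the record is neither a confirmed early termination nor unscheduled. SAP 10.4 is not reached, because Week 12 is no longer missing.

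**3. Timing example (assumed course).** Skin reaction at Day 15, maximum 14-day hold, restart on 15 + 14 = Day 29, flare and stop on Day 30.
- 85 − 30 = 55 days before the Week 12 target
- 72 − 30 = 42 days before the Week 12 window opens
- With a Study Exit form on that date, the record would map to Week 4 (Day 23 to 43)

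Day 30 also lies within the scheduled Week 4 visit (29 ± 5 = Day 24 to 34), so here the count might be recorded under Week 4 instead. That escape is not general: Days 35 to 51 lie between the Week 4 and Week 8 visits (57 − 5 = Day 52), and Days 63 to 79 between Week 8 (57 + 5 = Day 62) and Week 12 (85 − 5 = Day 80).

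**4. Effect on the primary response** (stop-day record dated before Day 72).

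| Scheduled Week 12 visit | Stop-day count | Using the stop-day record | Using the scheduled visit, or SAP 10.4 if missed |
|---|---|---|---|
| Missed | 0 | Responder | Nonresponder |
| Missed | above 0 | Nonresponder | Nonresponder |
| Attended, count above 0 | 0 | Responder | Nonresponder |
| Attended, count 0 | above 0 | Nonresponder | Responder |
| Attended, both 0 or both above 0 | – | Same | Same |

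The error can go either way. In the second row the primary response is unchanged, but the early value would still enter the exploratory Week 12 change-from-baseline analyses.

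**5. Size.** One subject: 1/227 = 0.44 points on SB206, or 1/113 = 0.88 on vehicle. The documents give no count of suspected contact dermatitis. For an assumed 0 to 3 misread subjects in one arm, the shift is 0 to 3/227 = 1.3 points on SB206, or 0 to 3/113 = 2.7 on vehicle.

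**The case against.** **The mechanism depends on an unseen form.** Section 7.2.4 names a set of procedures, not an eCRF visit. Table 1 permits unscheduled visits for medical reasons, and SAP 7 already handles those. The dataset specifications named in SAP Appendix C might also settle the choice, and they were not supplied. This stands: entry on the shared form is a condition. But the site is told to complete Week 12/ET1 assessments, and the SAP says one form serves both visits, so that entry is a natural one. If the form can be completed only once per subject, the Day 85 count has no defined place.

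**Few subjects, small effect.** Protocol 1.2.2 reports no adverse-event stops on 12% QD in Phase 2 (0 of 48). Harm also needs either a missed visit after a stop-day count of 0, or two discordant counts. This stands, and it limits the point to a clarification.

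**A sensitivity analysis already covers it.** SAP 10.4 and 11.1 plan an analysis that counts subjects clear at their last assessment as responders when Week 12 is missing. That would expose the missed-visit case only if the record were placed by study day. Under the Week 12 label nothing is missing, so the primary and sensitivity results agree for that subject. It does not resolve the two-record case.

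**The missed visit would be noticed anyway.** A reader might infer that the early record hides the deviation of a Week 12 count not being done. The documents do not support that. SAP 9.5 has deviations reviewed before unblinding and does not derive them from the analysis label, and Protocol 14.2 requires full verification of primary efficacy variables.

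**Conclusion.** The point holds conditionally. If stop-day assessments for suspected contact dermatitis are entered on the shared form, SAP 7 as written labels them Week 12 at any study day. The early count can then replace a missed Week 12 count, or compete with an attended one without a selection rule. Each misread subject is worth 0.44 points on SB206 or 0.88 on vehicle, against a planned difference of 18 points. The number affected may be zero.

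Two stronger readings are not supported:
- **Arm imbalance.** All seven adverse-event stops in Phase 2 were on active drug, which might suggest that the error falls on SB206. All seven were in BID groups and none was on the 12% QD regimen studied here.
- **Lost power.** The direction of the error is not fixed and its frequency is unknown, so no loss can be claimed.

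The clarification is still worth making, because the protocol itself prescribes this path and the record feeds the primary endpoint.

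**What to change.** Change SAP 7 only, before unblinding. After the sentence on records without a Study Exit form, add:

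> A Week 12/ET1 record completed at permanent treatment discontinuation in a subject who remains in the study (no Study Exit form on that date) is handled as an unscheduled visit under the window table, and is used for Week 12 only if it falls in Day 72 to 98 and the scheduled Week 12 visit has no lesion count. If the scheduled Week 12 visit has a count, that count is used.

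Two broader remedies would do harm. Taking whichever record is closest to Day 85 could prefer a stop-day count on Day 82 (3 days away) to an attended visit on Day 89 (4 days away). A blanket Day 72 cut-off could discard a genuine Week 12 visit held early. The wording above is limited to stop-day records and avoids both.

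The cost is one or two SAP sentences and a check of the affected records. That check can start from the narrative listing in SAP 6, which already includes skin reactions suggestive of allergic contact dermatitis. The protocol can stay as it is. Rewriting Sections 7.2.4 and 7.2.5 would require an amendment with IRB/IEC approval under Protocol 15, and the SAP sentence makes that unnecessary.
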